10.6.5. Efficacy

Post-ipratropium FEV1

- The difference between post-ipratropium FEV1 and pre-salbutamol FEV1 will be calculated.

Reversibility and GOLD Stage

- A subject's responsiveness to salbutamol at Screening will be classified as 'Reversible' or 'Non-reversible' based on the difference between their pre-salbutamol assessment of FEV1 and their post-salbutamol assessment of FEV1 as follows:
 - Reversible, if they had a difference in FEV1 of $\geq 12\%$ and $\geq 200\text{ mL}$, or
 - Non-reversible, if they had a difference in FEV1 of $< 200\text{ mL}$ or a $\geq 200\text{ mL}$ difference that was $< 12\%$ of the pre-salbutamol FEV1.
- A subject's responsiveness to salbutamol and ipratropium at Screening will be classified as 'Reversible' or 'Non-reversible' based on the difference between their pre-salbutamol assessment of FEV1 and their post-ipratropium assessment of FEV1 as follows:
 - Reversible, if they had a difference in FEV1 of $\geq 12\%$ and $\geq 200\text{ mL}$, or
 - Non-reversible, if they had a difference in FEV1 of $< 200\text{ mL}$ or a $\geq 200\text{ mL}$ difference that

was < 12 % of the pre-salbutamol FEV1.

- Subjects will be classified according to Global Initiative for Chronic Obstructive Lung Disease (GOLD) stage (GOLD classification, [GOLD, 2011]): defined using the post-salbutamol percent predicted FEV1 assessed at Screening (Visit 1). Subjects will be classified as:
 - GOLD1: Mild FEV1 \geq 80% predicted
 - GOLD 2: Moderate 50% \leq FEV1 < 80% predicted
 - GOLD3: Severe 30% \leq FEV1 < 50% predicted
 - GOLD4: Very Severe FEV1 <30% predicted

Trough FEV1 and FVC

- The trough value for FEV1 and FVC at each of Days 2, 28, 56, 84, 112, 168 and 169 is calculated from the values at the assessments made 23 h and 24 h after dosing on the previous day. If the actual time of an assessment is after the time of dosing on the current day, the value will not be used in the calculation of trough. For the PP population, a value will additionally be excluded from the trough calculation if the assessment is outside the time window of 22.5-24.5 h after dosing on the previous day (see Section 10.1.2 (Exclusions of Data from Per Protocol Analyses)). If one of the values is missing or excluded then the trough will be the single remaining value; otherwise the trough will be the mean of the two values.

BDI/TDI

- The baseline dyspnoea index (BDI) focal score will be calculated as the sum of the ratings recorded for each of the three individual scales (Baseline Functional Impairment, Baseline Magnitude of Task, Baseline Magnitude of Effort). Each of these scales has five possible scores ranging from 0 to 4 (with lower scores indicating more impairment), so the range of the BDI focal score is 0 to 12. If a score is missing (or has a value of W, X or Y) for any of the three scales, then the BDI focal score will be set to missing.
- The TDI focal score will be calculated as the sum of the ratings recorded for each of the three individual scales (Change in Functional Impairment, Change in Magnitude of Task, Change in Magnitude of Effort). Each of these scales has seven possible scores ranging from -3 (major deterioration) to +3 (major improvement), so the range of the TDI focal score is -9 to +9. If a score is missing (or has a value of Z) for any of the three scales, then the TDI focal score will be set to missing.
- A subject will be considered a 'responder' according to TDI at each visit if the TDI focal score was at least 1 unit at that visit. A subject will be considered a 'non-responder' if the score was less than 1 unit.
- For the classification of responders, subjects with missing TDI assessments will be handled as detailed in Section 10.7.2.1 (Handing of Missing Responder).

Weighted Mean FEV1 and FVC

- Weighted mean FEV1 and FVC will be calculated over the nominal 0-6 h post dose period. Values from post-dose assessments which are actually before the time of dosing will be excluded from the calculation.
- The 0 h value is the average value obtained 30 min and 5 min pre-dose, and both the 0 h and 6 h values must be present for a 0-6 h weighted mean to be calculated.
- The 0-6 h weighted mean will be derived by calculating the area under the FEV1 or FVC/time

Weighted Mean FEV1 and FVC

curve over the nominal time points of 0 h (as defined above), 15 and 30 min, 1, 3 and 6 h, using the trapezoidal rule, and then dividing by the actual time between dosing and the 6 h assessment. For post-dose observations the actual time of assessment relative to the time of dosing will be used for the calculation.

$$\text{Weighted Mean (0-6h)} = \left[\frac{1}{2} \sum_{i=1}^{I-1} (t_{i+1} - t_i)(y_i + y_{i+1}) \right] / [t_l - t_f]$$

where

y_i represents the value of the endpoint at the i th timepoint,

t_i represents the actual relative time at the i th timepoint,

t_f represents the actual relative time at the first timepoint ($t_f = 0$ as the pre-dose measurement is used),

t_l represents the actual relative time at the last timepoint (the 6h timepoint),

I represents the number of timepoints used in the AUC calculation.

If missing values are present in data required for the calculation of the weighted means, the following approach will be employed:

- If more than a third of the observations are missing then the weighted mean will be set to missing for that subject.
- If an observation is missing between two non-missing observations, the value will be interpolated between the two non-missing values.
- If there are two or more missing points that occur consecutively then the weighted mean will be set to missing.
- If the first time-point is missing then the weighted mean will be set to missing.
- If the last time-point is missing then the weighted mean will be set to missing.

Rescue Use

- For rescue use, 'day' refers to the period (24 hours) between one record of rescue use and the next in the database.
- The total puffs of rescue for each day will be calculated as number of salbutamol puffs. If the number of puffs are missing then the total puffs will be set to missing for that day.
- Rescue use will be summarised over the periods defined in below table:

| Period | First day | Last day |
|----------|---|----------------|
| Baseline | Latest of 6 days before Visit 2 and day after Visit 1 | Day of Visit 2 |
| Week 1-4 | Study day 2 (day after Visit 2) | Study day 29 |
| Week 5-8 | Study day 30 | Study day 57 |

| Rescue Use | | | |
|---|---------------------------------|--|--|
| Week 9-12 | Study day 58 | Study day 85 | |
| Week 13-16 | Study day 86 | Study day 113 | |
| Week 17-20 | Study day 114 | Study day 141 | |
| Week 21-24 | Study day 142 | Earliest of Study day 169 and day before Visit 9 | |
| Week 1-24 | Study day 2 (day after Visit 2) | Earliest of Study day 169 and day before Visit 9 | |
| 
 For each summary period, the mean number of puffs per day and the percentage of rescue-free days will be calculated, provided at least half the days within the summary period have non-missing values for the endpoint. Any data recorded after study day 169 (but before Visit 9) will not be included in any summaries. | | | |

| Time to Onset on Day 1 |
|--|
| 
 The time to onset on Day 1 is calculated as the time (both nominal and actual) that the first post-dose FEV1 during the 0-6 h post-dose period is ≥ 100 mL above baseline FEV1. Post-dose assessments that are actually pre-dose will be considered missing in the calculation. Subjects who have at least one FEV1 assessment within the 0-6 h post-dose period but do not achieve a ≥ 100 mL increase from baseline over 0-6 h post-dose will be considered censored. |

| Increase in FEV1 of $\geq 12\%$ and ≥ 200 mL above Baseline at any Time During 0-6 h Post-dose on Day 1 |
|--|
| 
 A flag will be derived to identify whether or not a subject achieved an increase in FEV1 of $\geq 12\%$ and ≥ 200 mL above baseline at any time during 0-6 h post-dose on Day 1. The flag will have values as follows: 
 1, if any FEV1 value recorded at 15 or 30 min, 1, 3 or 6 h was $\geq 12\%$ and ≥ 200 mL above baseline. 0, if no FEV1 value recorded at 15 or 30 min, 1, 3 or 6 h was $\geq 12\%$ and ≥ 200 mL above baseline. |

| Increase of ≥ 100 mL above Baseline in Trough FEV1 |
|--|
| 
 A flag will be derived to identify whether or not a subject achieved an increase of ≥ 100 mL above baseline in trough FEV1 at each of Days 2, 28, 56, 84, 112, 168 and 169. The flag will have values as follows: 
 1, if the trough FEV1 was ≥ 100 mL above baseline. 0, if the trough FEV1 was < 100 mL above baseline, or the trough FEV1 was missing with no subsequent non-missing trough FEV1 values. Missing, if the trough FEV1 was missing but subsequent trough FEV1 values were non-missing. |

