Inhaled short-acting anticholinergics ² (e.g. ipratropium bromide)	4 hours (stable dose of ipratropium alone is allowed during the study, provided that the subject is on a stable dose regimen from Screening (Visit 1 and remains so throughout the study) but must be withheld 4 hours prior to each study visit)
Inhaled short-acting anticholinergic/short-acting beta ₂ -agonist combination products	4 hours

Medication	Time Interval Prior to Visit 1
Any other investigational drug	30 days or 5 half lives, whichever is longer

1. Use of ICS is permitted provided the dose not exceed 1000mcg of fluticasone propionate or equivalent; ICS use not to be initiated or discontinued within 30 days prior to Visit 1
2. Ipratropium bromide or theophylline is permitted, provided that the subject is on a stable dose from Screening (Visit 1) and remains on the stable dose throughout the study; however, Ipratropium bromide must be withheld for 4 hours; theophylline must be withheld for 12 hours prior to and during each clinic visit.
3. The dose of ICS must be equivalent to that contained in the ICS/LABA combination product (the study procedures manual will have equivalence guidelines)
4. Use of study provided albuterol/salbutamol is permitted during the study, except in the 4-hour period prior to spirometry testing

13. Oxygen: Use of long-term oxygen therapy (LTOT) described as oxygen therapy prescribed for greater than 12 hours a day. As-needed oxygen use (i.e., \leq 12 hours per day) is not exclusionary.

14. Nebulized Therapy: Regular use (prescribed for use every day, not for as-needed use) of short-acting bronchodilators (e.g., albuterol/salbutamol) via nebulized therapy.

15. Pulmonary Rehabilitation Program: Participation in the acute phase of a pulmonary rehabilitation program within 4 weeks prior to Visit 1. Subjects who are in the maintenance phase of a pulmonary rehabilitation program are not excluded.

16. Drug or Alcohol Abuse: A known or suspected history of alcohol or drug abuse within 2 years prior to Visit 1.

17. Affiliation with Investigator Site: Is an investigator, sub-investigator, study coordinator, employee of a participating investigator or study site, or immediate family member of the aforementioned that is involved in this study.

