5. STUDY TREATMENTS

5.1. Investigational Product and Other Study Treatment

GlaxoSmithKline (GSK) will provide the investigational product for use in this study. The investigational product Umeclidinium Inhalation Powder (62.5 mcg), and Placebo Inhalation Powder will each be delivered via an ELLIPTA.

Each ELLIPTA will be comprised of one or two foil, laminate, blister strip/s. Descriptions of the double-blind investigation product for this study are provided in [Table 2](#) (Umeclidinium) and [Table 3](#) (placebo).

The ELLIPTAs containing investigational product and placebo will be identical in appearance. Subjects will be instructed to take one inhalation each morning from their ELLIPTA. Subject instructions and details on how to use the ELLIPTA are provided in the SPM.

All subjects will receive supplemental albuterol/salbutamol (MDI and/or nebulus) to be used on an as-needed basis (rescue medication) throughout the study. Albuterol/salbutamol will be sourced from local commercial stock. If not available locally, GSK will source centrally.

Ipratropium bromide MDI for additional responsiveness testing at Visit 1 will be sourced from local commercial stock. If not available locally, then GSK will source centrally.

Table 2 Description of Umeclidinium Inhalation Powder ELLIPTA

Formulation	First strip
	Umeclidinium bromide blended with lactose monohydrate and magnesium stearate ¹
Dosage Form	ELLIPTA with 30 doses (1 strip with 30 blisters)
Unit Dose Strengths	62.5 mcg
Physical Description	White powder
Route of Administration	Inhaled

1. Magnesium stearate 0.6% w/w of total drug product

Table 3 Description of Placebo Inhalation Powder ELLIPTA

Formulation	First strip	Second strip
	Lactose monohydrate blended with magnesium stearate ¹	Lactose monohydrate blended with magnesium stearate ²
Dosage Form	ELLIPTA Inhaler with 30 doses (2 strips with 30 blisters per strip)	
Unit Dose Strengths	Not applicable	Not applicable
Physical description	White powder	White powder
Route of Administration		Inhaled

1. Magnesium stearate 0.6% w/w of total drug product

2. Magnesium stearate 1.0% w/w of total drug product

The contents of the label will be in accordance with all applicable regulatory requirements.

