5.6. Concomitant Medications and Non-Drug Therapies

All COPD medications used within 30 days prior to visit 0 and onward should be recorded in the eCRF including any changes. Beginning at visit 1 and throughout the rest of the study, all non COPD medications taken during the study will be recorded in the eCRF, including any changes. Study-provided albuterol/salbutamol should not be recorded in the eCRF. The minimum requirement includes but is not limited to drug name, dose, route and the dates of administration. Medications initiated after completion of Visit 9 or the Early Withdrawal Visit will not be recorded in the eCRF with the exception of those used to treat a COPD exacerbation or SAE that occurs between Visit 9 (or the Early Withdrawal Visit) and the follow-up contact.

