6.2.3. Other Endpoints

Other endpoints include:

- Trough FEV₁ and mean TDI score at other time points
- Rescue albuterol/salbutamol use (percentage of rescue-free days and puffs/day)
- Time to onset (defined as an increase of 100mL in FEV₁ above baseline) during 0 to 6h post-dose on Treatment Day 1 (Visit2)
- Proportion of subjects achieving an increase in FEV₁ of $\geq 12\%$ and $\geq 200\text{mL}$, above baseline at any time point during 0 to 6h post-dose on Treatment Day 1 (Visit 2)
- Proportion of subjects achieving an increase in FEV₁ of $\geq 100\text{mL}$ above baseline in trough FEV₁
- Serial FEV₁ over 0 to 6 hours post-dose at Visit 2 (Day 1)
- Serial and Trough FVC
- Proportion of responders to TDI. A responder to TDI will be defined as a subject who reported a TDI score of 1 unit or more.
- Time to first COPD exacerbation

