6.2.6. Diary Assessments

6.2.6.1. Paper Diary

Subjects will use paper diary to record the following information:

- Any medical problems experienced and any medications used to treat those medical problems. These entries will be reviewed by the study coordinator at each study visit and recorded in the eCRF as an adverse events/concomitant medication or COPD exacerbations as appropriate.

- The date and time of the morning dose of study medication taken on the days prior to Visit 4, Visit 5, Visit 6, Visit 7, and Visit 8
- Supplemental albuterol/salbutamol used over the previous 24 hours.

Subjects will be asked to bring the paper diary to each clinic visit. The study coordinator will review the paper diary at each clinic visit for completeness, legibility and consistency with subject-reported AEs. Signs and symptoms of COPD recorded on the diary card will not be considered AEs and will not be collected in the eCRF. Additional details for completion of the diary cards are provided in the SPM.

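### Rescue salbutamol may be supplied as inhaler and/or nebules, but the SAP counts only puffs and has no rule for a day of nebule use

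*SAP*

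**What the plan says.** - **Supply.** Protocol 5.1: "All subjects will receive supplemental albuterol/salbutamol (MDI and/or nebulus) to be used on an as-needed basis (rescue medication) throughout the study". The last form named in the bracket is read here as nebules.
- **What is barred.** Exclusion criterion 14 (Protocol 4.3) covers "Regular use (prescribed for use every day, not for as-needed use) of short-acting bronchodilators" by nebuliser, and Protocol 5.6.2 prohibits regular nebulised therapy during the study. Neither bars as-needed nebules.
- **Diary.** Protocol 6.2.6.1 has subjects record "Supplemental albuterol/salbutamol used over the previous 24 hours". It gives no unit and no split by form, and refers completion details to the Study Procedures Manual (SPM).
- **Derivation.** SAP 10.6.5 (Rescue Use): "The total puffs of rescue for each day will be calculated as number of salbutamol puffs". It adds: "If the number of puffs are missing then the total puffs will be set to missing for that day". Mean puffs per day and percentage of rescue-free days are then computed for each period, "provided at least half the days within the summary period have non-missing values for the endpoint".
- **Concomitant medication.** Protocol 5.6: "Study-provided albuterol/salbutamol should not be recorded in the eCRF".
- **Status.** Rescue use is among the other endpoints (Protocol 6.2.3). SAP 7.3.2.4 analyses puffs per day by ANCOVA. SAP Table 5 marks rescue-free days for summary only. SAP 10.11 calls comparisons on such endpoints exploratory.

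**The concern.** Two forms of rescue are allowed and one is counted. The SAP has no nebule count, no conversion to puffs and no statement that a nebule day is not rescue-free. In fact it never defines a rescue-free day; zero total puffs is the implied meaning. A subject who needed a nebule but took no puffs would therefore be credited with a rescue-free day, or would lose that day from the period value. Either way, days of real rescue use fall out of two named efficacy endpoints. One of these, puffs per day, is reported with treatment differences, confidence intervals and p-values for each four-week period and for the full 24 weeks. The same derivation feeds the baseline covariate. The concomitant-medication record cannot fill the gap, because study-supplied salbutamol is kept out of it.

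**Working it through.** The plan gives no figure for the rescue endpoints to reproduce, so the check applies the SAP rule to assumed days.

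**One subject, one period.** Weeks 1-4 run from study day 2 to day 29: 29 − 2 + 1 = 28 days. Assume 10 puff days at 2 puffs each, k nebule-only days, and the remaining 18 − k days truly free of rescue. The documents give no conversion, so each nebule-only day is assumed to be worth e = 2 to 8 puffs. This range is for illustration only.

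- True: rescue-free (18 − k)/28; puffs per day (20 + k·e)/28.
- Nebule-only days scored zero: rescue-free 18/28; puffs per day 20/28.
- Nebule-only days missing: rescue-free (18 − k)/(28 − k); puffs per day 20/(28 − k), if at least 14 days remain.

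| | True | Scored zero | Missing |
|---|---|---|---|
| k = 3, rescue-free | 15/28 = 53.6% | 64.3% | 15/25 = 60.0% |
| k = 3, puffs/day | 26/28 to 44/28 = 0.93 to 1.57 | 0.71 | 20/25 = 0.80 |
| k = 7, rescue-free | 11/28 = 39.3% | 64.3% | 11/21 = 52.4% |
| k = 7, puffs/day | 34/28 to 76/28 = 1.21 to 2.71 | 0.71 | 20/21 = 0.95 |

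At k = 15 only 13 days remain under missing coding, and the period value is lost. Under zero coding both errors always go the same way: too many rescue-free days and too few puffs. Under missing coding, puffs per day is understated whenever a nebule-only day is worth more than the mean of the recorded days, as it is throughout this range. On a day with both puffs and nebules, the day is correctly not rescue-free and only the puff total is short.

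**Between arms.** Let n be the proportion of all days that are nebule-only. Zero coding adds n to each arm's rescue-free proportion and takes e·n from its puffs per day. The difference between arms therefore shifts only by the difference in n. Missing coding with equal n leaves no shift but divides the rescue-free difference by 1 − n. For example, at n = 5%, 50/95 − 40/95 = 10.5 points instead of 10.

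Assume true rescue-free days of 50% on UMEC and 40% on placebo, so rescue days are 50% and 60%:

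| Nebule-only share of rescue days | n, UMEC / placebo | Difference, scored zero | Difference, missing |
|---|---|---|---|
| 10% in both arms | 5% / 6% | 55 − 46 = 9 points | 50/95 − 40/94 = 52.6 − 42.6 = 10.1 points |
| 10% UMEC, 20% placebo | 5% / 12% | 55 − 52 = 3 points | 50/95 − 40/88 = 52.6 − 45.5 = 7.2 points |

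For puffs per day with zero coding, the shift is e × (difference in n). This is 0.01 × 2 to 0.01 × 8 = 0.02 to 0.08 in the first case, and 0.07 × 2 to 0.07 × 8 = 0.14 to 0.56 in the second.

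**The case against.** **Data capture is not visible.** The SPM and eCRF version 1.3, on which the SAP is based, are not available. Either might convert nebules to puffs before the SAP rule applies, or only MDIs might be dispensed. This stands, and it makes the consequence conditional. It does not supply the missing rule, since neither document mentions a conversion.

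**The SAP follows the protocol's unit.** The protocol itself names the endpoint as puffs per day. That is fair for the puff total. It does not answer for rescue-free days, which need no unit and only require knowing whether any rescue was taken.

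**The stakes are low.** Both endpoints are exploratory, and no primary or secondary conclusion depends on them. This stands and sets the severity.

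**A stronger reading is tempting.** A reader might infer that nebules mark the most breathless days, that placebo subjects use more of them, and that the rescue benefit is therefore diluted, say from 10 points to 3. The documents do not support this. They give no rate of nebule use, overall or by arm, and do not link nebules to worse days. The fall to 3 points needs both zero coding and an assumed two-fold imbalance in the nebule-only share. It also concerns a difference in rescue-free days, which the SAP does not model.

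**Conclusion.** The mismatch between Protocol 5.1 and SAP 10.6.5 is in the current text of both documents, and nothing else in either repairs it. Unless nebules are converted at capture, rescue-free days are overstated and puffs per day understated for subjects who use nebules. In the illustration, 3 nebule-only days in 28 overstate rescue-free days by 10.7 points (64.3 − 53.6) if scored zero, or 6.4 points (60.0 − 53.6) if missing. Those day counts are assumptions; the actual size is unknown and is nil if nebules are not used. A shift in the treatment comparison further requires nebule use to differ by arm, about which the documents say nothing. It would be going too far to say that the rescue results are wrong, or that they are biased in a known direction between arms. The primary endpoint is unaffected. Severity: minor.

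**What to change.** Before unblinding, establish which forms were dispensed and how nebule use reaches the database, then reconcile the two sections.

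- **If nebules are supplied:** in SAP 10.6.5, define a rescue-free day as zero puffs and zero nebules. For puffs per day, either pre-specify a puff-equivalent per nebule, used for analysis only, with a sensitivity run that varies it, or report nebule days separately. Apply the same rule to the baseline period. Confirm that the diary and eCRF capture nebule use.
- **If only MDIs are supplied:** correct Protocol 5.1 and leave the derivation as it is.

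The SAP text is short. The puff-equivalent is a convention, so puffs per day will depend on it; the rescue-free definition needs no conversion. If nebule counts are not already collected, adding them means changing the diary and eCRF, and past days cannot be recovered. In that case the report should state the limitation.
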